5.2.3 Safety Analysis Set

The Safety Analysis Set (SafAS) is defined as those subjects who have received study vaccine. All subjects will have their safety analyzed according to the vaccine they actually received. Safety data recorded for a vaccine received out of the protocol design will be excluded from the analysis (and listed separately).

5.2.4 Populations Used in Analyses

The primary immunogenicity analyses will be performed on the FAS, and will be confirmed on the PPAS. In the FAS, subjects will be analyzed by the vaccine group to which they were randomized.

The SafAS will be performed on the safety analysis set.

5.3 Handling of Missing Data and Outliers

5.3.1 Safety

No replacement will be done. All subjects with safety data and all safety data recorded in the eCRFs will be included in the safety analyses.

In all subject listings, partial and missing data will be clearly indicated as missing.

5.3.1.1 Immediate

For unsolicited non-serious systemic AEs, a missing response to the “Immediate” field is assumed to have occurred after the 30-minute surveillance period and will not be imputed.

For SAEs, missing or partially missing elapsed time from last vaccination recorded if within 24 hours will be assumed to have occurred after the 30-minute surveillance period and will not be imputed. Such SAEs will not be considered as immediate.

5.3.1.2 Causality

Missing causality (relationship) for unsolicited non-serious AEs and SAEs will be considered at the time of analysis as related to vaccination.

5.3.1.3 Measurements

Partially missing temperatures will be handled as described in Section 4.4.1.1.1.

5.3.1.4 Intensity

For solicited reactions, missing intensities will be handled as described in Section 4.4.1.1.1. For unsolicited non-serious AEs, missing intensities will remain missing and will not be imputed.

5.3.1.5 Start Date and Stop Date

Missing or partially missing start dates for unsolicited non-serious AEs will remain missing and not be imputed. If the start date is missing or partially missing, the time of onset will be considered to be missing. Nevertheless unsolicited AEs with missing time of onset will be included in analyses according to the visit collected.

Since SAEs are not collected by visit, though missing or partially missing start dates will not be imputed, logic will be applied to determine whether the event started between D0 to D30 or between D31 to 6-month follow-up contact.

Missing or partially missing stop dates for AEs (solicited reactions and unsolicited AEs) will remain missing and not be imputed.

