4.4.1.2.3 Time of Onset

Time of onset is derived from the start date of the unsolicited non-serious AE provided in the clinical database and the date of last vaccination:

- start date of the unsolicited non-serious AE minus date of previous vaccination

The time of onset should be considered as missing only if one or both of the dates are missing or partially missing.

The unsolicited non-serious AEs will be analyzed “Within 30 days”, which corresponds to AEs with a time of onset between 0 and 30 days after vaccination or missing. An AE with missing time of onset will be considered to have occurred just after the vaccination indicated by the visit number, so will be included in these tables.

Note: Unsolicited non-serious AE that occurred before vaccination (negative time of onset) or with a time of onset will not be included in analysis, but will be listed separately.

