5.1.3.2.2 Safety

The number and percentage of subjects reporting any solicited injection site reactions and solicited systemic reactions will be summarized by study group, intensity (Grade 1, Grade 2, and Grade 3), and period (D0 to D3, D4 to D7, and D0 to D7 after vaccination) for each reaction term. For a time period in which more than 1 intensity was recorded, the highest intensity will be used. Exact (Clopper-Pearson) 2-sided 95% confidence intervals (CIs) will be calculated for the percentages.

Immediate reactions, unsolicited AEs (including MAAEs), and SAEs will be coded and presented by MedDRA preferred term and system organ class (SOC). The number and percentage of subjects reporting safety findings will be summarized by study group for each preferred term, and SOC that has at least 1 report, as well as by relationship to study vaccine. SAEs will be tabulated separately from D0 through the end of the 6 month follow-up. Unsolicited AEs representing a change in the health status of the subject will be presented from D0 through D30. MAAEs will be presented from V01 through V02 through the end of the 6-month follow-up period.

Descriptive statistics will include, but not be limited to:

Table 5.1: Statistical analyses for safety observational objective

Safety Events	Time and Group	Description
Immediate unsolicited systemic AE	Within 30 minutes after injection for all subjects in Groups 1 - 6 at D0	Percentage of subjects that have the event, MedDRA terms, intensity, relationship to vaccine, study discontinuation, duration
Extensive limb swelling	Up to 7 days after D0 for all subjects in Groups 1 – 6	Percentage of subjects that have the event
Solicited injection site reactions	Up to 7 days after D0 for all subjects in Groups 1 – 6	Percentage of subjects that have the event, time of onset, duration, intensity, action taken, study discontinuation, number of days of occurrence
Solicited systemic reactions	Up to 7 days after D0 for all subjects in Groups 1 – 6	
Unsolicited AE	Up to 7 days after D0 for all subjects in Groups 1 – 6 From D0 to D30 for all subjects in Groups 1 – 6	Percentage of subjects that have the event, MedDRA terms, time of onset, duration, intensity, relationship, action taken, study discontinuation

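### Unsolicited non-serious AEs with a known start month but no day are counted just after vaccination, even when the month rules that out

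*SAP*

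**What the plan says.** SAP 5.3.1.5 opens with "Missing or partially missing start dates for unsolicited non-serious AEs will remain missing and not be imputed" and continues: "If the start date is missing or partially missing, the time of onset will be considered to be missing". SAP 4.4.1.2.3 has the matching definition: "The time of onset should be considered as missing only if one or both of the dates are missing or partially missing". A start date with month and year but no day is therefore handled exactly like a blank one.

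On placement, SAP 4.4.1.2.3 defines the 30-day analysis as one "which corresponds to AEs with a time of onset between 0 and 30 days after vaccination or missing" and adds: "An AE with missing time of onset will be considered to have occurred just after the vaccination indicated by the visit number". SAP 5.3.1.5 puts it differently: "Nevertheless unsolicited AEs with missing time of onset will be included in analyses according to the visit collected".

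SAP Table 5.1 reports unsolicited AEs over two windows, D0-D30 and "Up to 7 days after D0 for all subjects in Groups 1" to 6. Collection runs to V02, which may fall anywhere from D30 to D44 (SAP 3.1), or to D37 in the CMI subset (SAP Table 3.2, footnote). SAP 4.4.1.2.3 removes pre-vaccination AEs from the tables and lists them separately, but identifies them by a negative time of onset.

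**The concern.** A conservative placement makes sense when nothing is known about timing. Here something is known and is set aside. If the recorded month contains no day of the window, the event cannot belong there, yet the rule still counts it. The safeguard for pre-vaccination events fails for the same reason: a partial date yields no onset value, so it can never yield a negative one.

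The D0-D7 table has a further gap. SAP 4.4.1.2.3 names only the 30-day analysis before referring to its tables in the plural. Entry into D0-D7 follows from treating the event as occurring right after vaccination, but the SAP never says so.

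Early unsolicited AE rates are among the descriptive safety results for formulations tested in humans for the first time (Protocol 5.1.2), and Protocol 1.4 says safety data will help decide which formulation advances to Phase III. The stake is the accuracy of those rates. Neither alert threshold given in the Protocol synopsis depends on this rule: extensive limb swelling is a solicited reaction, and related life-threatening events or deaths are SAEs.

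**Working it through.** The plan states no figure to reproduce here, so the check is on dates.

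**Inputs**
- Windows: D0-D7 and D0-D30 (SAP Table 5.1).
- Last day of collection: V02 on D30 to D44 (SAP 3.1); D30 to D37 in the CMI subset.
- Adult vaccination dates: October to December 2015 (Protocol 5.1.5), taken as 92 equally likely days.
- Assumptions: onset is equally likely on each day from D0 to V02, and the day of the month is lost regardless of when onset fell.

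**Step 1: single cases**
- Vaccinated 1 Oct 2015: D7 is 8 Oct, D30 is 31 Oct, D44 is 14 Nov. An AE dated only Nov 2015 began on D31 or later, but is counted in D0-D30.
- Vaccinated 20 Oct 2015: D7 is 27 Oct, D30 is 19 Nov. An AE dated only Nov 2015 cannot lie in D0-D7, but would be placed there.
- Vaccinated 20 Nov 2015: an AE dated only Oct 2015 precedes vaccination. No negative onset can be computed, so the listing-only rule does not apply.

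**Step 2: how often the month alone excludes a window**

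For every vaccination date and every onset day after the window, keep only month and year, and check whether that month contains any day of the window. This gives the share excluded among onsets after the window. Multiply by the fraction of collected onsets that fall after the window: (V02 − 7)/(V02 + 1) for D0-D7, and (V02 − 30)/(V02 + 1) for D0-D30.

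| V02 on | Excluded from D0-D7, of all month-only AEs | Excluded from D0-D30, of all month-only AEs |
|---|---|---|
| D30 | 39.1% × 23/31 = 29.0% | none (no onset after D30 is collected) |
| D37 | 50.5% × 30/38 = 39.9% | 13.0% × 7/38 = 2.4% |
| D44 | 59.9% × 37/45 = 49.3% | 24.5% × 14/45 = 7.6% |

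The shares before multiplication differ by at most 0.2 percentage points for the planned adolescent and older-adult inclusion periods. With V02 on D44, every vaccination date allows at least one month-only AE to be wrongly placed in D0-D7, and about 46% of dates allow one to be wrongly placed in D0-D30.

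**Step 3: weight of one subject**

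1/225 = 0.44 percentage points for a formulation; 1/75 = 1.33 points for a formulation within an age group.

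The total effect is (number of month-only AEs) × (share in Step 2) × (weight in Step 3). The documents do not give the first factor. No share is calculated for pre-vaccination events, because nothing in the documents indicates how often such events would be recorded.

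**The case against.** The strongest reply is that the rule is prespecified, identical in all six groups and errs towards counting events, in a study that tests no hypothesis (SAP 5.1.3.1). Partial dates should also be uncommon. The diary is reviewed in person at V02 (Protocol 5.1.4), missing or discrepant entries are clarified verbally (Protocol 13.2), and a blind data review precedes lock (SAP 5.6). For the defined endpoint, AEs through 30 days, the month rules out the window for at most about 8% of partial-date events. All of this stands, and it limits the size of the problem. It does not justify counting an event where its own recorded month shows that it cannot be.

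Four stronger readings are tempting, and the documents do not support them.
- A reader might infer that undated MAAEs recalled at the 6-month call flood the early tables. The 30-day wording in SAP 4.4.1.2.3 could be read that way. However, 5.3.1.5 assigns events by the visit at which they were collected, Table 5.1 has a separate MAAE row from V02 onward, and the heading of 4.3.1.3.3 ends unsolicited non-serious AEs at V02. What remains is a difference in wording to be aligned.
- A reader might infer that many pre-vaccination events get in. The diary is issued after vaccination, and pre-existing conditions are not to be reported as AEs (SAP 4.3.1.1).
- A reader might infer that the listings hide the known month. SAP 5.3.1 says "In all subject listings, partial and missing data will be clearly indicated as missing"; it does not say that the recorded part is suppressed.
- A reader might infer that SAEs are consistently handled better. SAP 5.3.1.5 does promise date logic for them, giving as its reason that SAEs are not collected by visit. But SAP 4.4.1.3.2 also places SAEs with missing onset just after vaccination.

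**Conclusion.** The point holds as a defect in a stated rule, and its effect is probably small. Entry into D0-D30 is explicit in SAP 4.4.1.2.3; entry into D0-D7 is an inference, and the SAP should settle it. D0-D7 is the more exposed table: the month alone excludes it for about 40% to 49% of month-only AEs collected at V02 on D37 to D44, against about 2% to 8% for D0-D30. These shares rest on uniform vaccination dates and uniform onset, and they apply only to AEs whose day is missing. How many such AEs there will be is unknown, so no total number of subjects or percentage points can be claimed. Because the rule is common to all groups and inflates rather than hides events, nothing in the documents points to a bias between groups.

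**What to change.** In SAP 4.4.1.2.3 and 5.3.1.5:
- For a partial start date, derive the earliest and latest possible onset from the recorded month and year, with the upper limit capped at the visit or call where the AE was collected.
- If the latest possible onset precedes vaccination, list the event only.
- Otherwise count the event in D0-D7 or D0-D30 only when its possible range overlaps that window. Conservative placement is kept wherever the date leaves doubt.
- Keep the present rule for wholly missing dates collected at V02, and state outright whether these enter D0-D7.
- Align the two sections so that MAAEs collected at the 6-month call with no date go to the V02-to-6-month period.

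The cost is a few lines of SAP text and one extra derivation step, with no new data. Counts in the early windows would be slightly lower.

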5.3.2 Immunogenicity

For the calculation of GMCs and seroprotection, any pre-vaccination or post-vaccination titer reported as < LLOQ will be converted to a value of 0.5 LLOQ. For the calculation of 4-fold rise, any pre-vaccination value reported as < LLOQ will be converted to LLOQ, and any post-vaccination titer reported as < LLOQ will be converted to a titer of 0.5 LLOQ when only either the numerator or the denominator is < LLOQ. If both numerator and denominator are < LLOQ, then both will be converted in the same way so that the 4-fold rise is defined as 1. Any titer reported as > ULOQ (upper limit of quantitation) will be converted to ULOQ.

Missing data will not be imputed. No test or search for outliers will be performed.

5.3.3 Efficacy

No efficacy data was collected for this study.

5.4 Interim / Preliminary Analysis

No interim analyses are planned. An initial internal safety review (ESDR) for this study is planned when all adult subjects have been vaccinated and have provided safety data for V01 through V02 post-vaccination, using the data collection methods described in the protocol. The safety data collected will be entered into the electronic case report forms (eCRFs), and will be summarized and reviewed in a per-group partially blinded (group unblinded) fashion by the Sponsor. It is understood that this review will be based on preliminary data that have not been subject to validation and database lock. No statistical adjustment is necessary because no hypotheses will be tested.

5.5 Determination of Sample Size and Power Calculation

Although there are no statistically powered hypotheses in this study, the overall study cohort (N=1350) will provide a probability of approximately 93% of observing any AE with a true incidence of 0.2%. For each formulation (N=225), there is a probability of approximately 95% of

observing any AE with a true incidence of 1.3%, and a probability of approximately 36% of observing any AE with a true incidence of 0.2%.

Assuming a drop-out rate of approximately 10%, a total of 67 evaluable subjects per group is anticipated.

5.6 Data Review for Statistical Purposes

A blind review of the data has been anticipated through the data review process led by data management before database lock. This review of the data is anticipated to include a statistical review.

5.7 Changes in the Conduct of the Trial or Planned Analyses

The protocol does not mention a preliminary analysis. A partial database lock and a preliminary analysis will be done on safety and immunogenicity data for V01 to V02 before the 6-month follow-up data is locked, but data from V01 through the 6-month follow-up will be included in the same CSR.

6 References List

- 2 Newcombe R.G., Two-sided confidence intervals for the single proportion: comparison of seven methods, *Stat. Med.*1998; 17: 857-72.

Document Number CLI_1728718	Version Number 2.0
Project Code SP0173	
Document Name Statistical Analysis Plan	

	Approver Name	Date (Universal Time)	Reason for Signature
Approval	██████████ ██████████ ██████████ (sanofi pasteur)	19 Dec 2016 20:42:43	I am approving this document
Approval	██████████ ██████████ (I3 Statprobe)	19 Dec 2016 21:30:09	I am approving this document
Approval	██████████ ██████████ (sanofi pasteur)	20 Dec 2016 19:19:15	I am approving this document
Approval	██████████ ██████████, ██████████ (sanofi pasteur)	20 Dec 2016 23:02:57	I am approving this document as an author
